(3) Description of Study Treatments or Exposures/Predictors

Families that agree to participate in the study will be assigned a number (either one or two) from a random number generator. This will determine whether they are assigned to the PIRA (intervention) group or to the standard education (control) group.

Participants (children and their parents) will not be blinded to the study group (they will know if they received the PIRA). On the day of surgery, the research team member observing enrolled children for signs of anxiety in the preoperative area and the PACU nurse observing the children as they awaken from anesthesia post-operatively will be blinded to group assignment; they will not know, nor will they ask families, about their preoperative education experience.

Intervention Group: If assigned to the intervention group, families will receive access to the PIRA for a minimum of two days in addition to the standard of care pre-op education provided for all families (described below for the control group). The child's first name and age will be entered into the PIRA's enrollment page so that the tool can address the child by name and educate them in an age-appropriate manner. After an account has been created, an email containing instructions on the purpose of PIRA and how to use the program (Appendix A) will be sent to the email address provided by the family from a research team member at a BCH. Included in this email will be a hyperlink to access the PIRA, as well as a unique username and password for families to log in. Once enrolled, the PIRA will be accessible to the family as often and for as long as desired up to 10 days prior to the scheduled surgery. Parents will receive a reminder email a few days prior to their child's surgical date prompting them to log-in and complete the PIRA with their child at least once before the procedure. The parents will be encouraged to reach out to the Principal Investigator at any time if they have difficulty accessing the PIRA or if questions arise regarding the educational content within the program.

Control group: Participants assigned to the control group will receive the standard of care preoperative education at BCH Waltham. These participants will not receive any

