To determine any effect this PIRA may have on ED, the PACU RN assigned to care for the given patient will assess emergence upon patient arrival to PACU using the PAED scale. See Figure 3 for PAED Scale. The PAED is a routine assessment conducted by PACU RNs at Waltham for all post-operative pediatric patients upon emergence from anesthesia. A member of the research team will retrospectively extract the PAED score from the patient's chart. The PAED scale measures five behaviors, each rated on a five-point scale of zero to four. The scores are summed for total scale score up to a maximum value of 20 (Sikich & Lerman, 2004). An assessment of the internal consistency and reliability of the PAED scale validated it for assessing ED in children recovering from general anesthesia (Ringblom et al., 2018). A PAED ≥ 10 yields 64 percent sensitivity and 86 percent specificity (Sickich & Lerman, 2004), and a score of >12 yields 100 percent sensitivity and 94.5 percent specificity for the diagnosis of ED (Bajwa et al., 2010). For use in this study, ED will be considered present with a score ≥ 12 .

(6) Study Timeline

This study will take approximately one year to complete after IRB approval.

E. Adverse Event Criteria and Reporting Procedures

This is a minimal risk study. Any adverse effects associated with this study will be reported to the BCH IRB by the Principle Investigator (PI). If participants experience any adverse event related to this study and need follow-up for any concerns, they may be referred to the Patient Relations Department or Social Work Department at BCH as indicated.

F. Data Management Methods

All collected survey data as well as pre-op and PACU observation data will be de-identified and presented in aggregate, stored in REDCap® and kept in password-protected folders on BCH computers, accessible only by the research team members. The data collected directly from the PIRA program itself will be stored on a secure Northeastern University Server, and will be accessible only to the study team. Upon completion of data collection, the PIRA data will be transmitted back to BCH electronically and stored on the BCH server. All research team members will have completed CITI training.

G. Quality Control Method

Qualitative, free-text data will be analyzed by two or more members of the research team to ensure validity and concurrence of identified themes.

H. Data Analysis Plan

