20. I feel pleasant				

1: Not at all, 2: Somewhat, 3: Moderately so, 4: Very much so

Figure 3. PACU Pediatric Anesthesia Emergence Delirium (PAED) for Anesthesia**Emergence Delirium**

Behavior	Not at all	Just a little	Quite a bit	Very much	Extremely
The child makes eye contact with the caregiver	4	3	2	1	0
The child's actions are purposeful	4	3	2	1	0
The child is aware of his/her surroundings	4	3	2	1	0
The child is restless	0	1	2	3	4
The child is inconsolable	0	1	2	3	4

K. References

- Akdağ, M. (2014). A multi-centric prospective study: Anxiety and associated factors among parents of children undergoing mild surgery in ENT. *Journal of Clinical and Experimental Investigations*, 5(2), 206–210.
- Aytekin, A., Doru, Ö., & Kucukoglu, S. (2016). The effects of distraction on preoperative anxiety level in children. *Journal of Perianesthesia Nursing: Official Journal of the American Society of Peranesthesia Nurses / American Society of Peranesthesia Nurses*, 31(1), 56–62.
- Bartik, K., & Toruner, E.K. (2017). Effectiveness of a preoperative preparation program on children's emotional states and parental anxiety. *Journal of Perianesthesia Nursing: Official Journal of the American Society of PeriAnesthesia Nurses / American Society of PeriAnesthesia Nurses*. <https://doi.org/10.1016/j.jopan.2017.09.008>
- Beringer, R. M., Greenwood, R., & Kilpatrick, N. (2013). Development and validation of the Pediatric anesthesia behavior score - an objective measure of behavior during induction of anesthesia. *Pediatric Anesthesia*, 24(2), 196–200.

- Buckley, A., & Savage, E. (2010). Preoperative information needs of children undergoing tonsillectomy. *Journal of Clinical Nursing*, 19(19-20), 2879–2887.

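### A quiet child who is not yet awake scores exactly 12 on the PAED as printed, which meets the ED definition of ≥ 12, and the plan neither fixes the scoring time nor requires the child to be awake

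*Combined protocol and SAP*

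**What the plan says.** ED is a secondary outcome, reported as present or absent. Section D(5), under emergence from anesthesia, has the PACU nurse score the PAED, and the research team later extracts the score from the chart. The definition reads: "For use in this study, ED will be considered present with a score" ≥ 12. Table 1 gives the same threshold and names only the PACU as the setting.

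The time of scoring is described in three ways:
- D(5): the nurse "will assess emergence upon patient arrival to PACU using the PAED scale".
- D(5), next lines: the PAED is a routine nursing assessment made when the child emerges from anesthesia.
- D(3): the blinded assessor is "the PACU nurse observing the children as they awaken from anesthesia post-operatively".

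Figure 3 prints the items. Three are reverse-scored, so the Not at all column carries 4 points: "The child makes eye contact with the caregiver", "The child's actions are purposeful" and "The child is aware of his/her surroundings". Two are scored forward, so Not at all carries 0: "The child is restless" and "The child is inconsolable". D(5) sums the five items to a maximum of 20.

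Just before adopting ≥ 12, D(5) cites 100% sensitivity and 94.5% specificity for a score of > 12. Nothing in the protocol requires the child to be awake, says how a sleeping child is handled, or says which charted score is taken if there are several.

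**The concern.** D(4) describes ED as a distressing state with flailing, kicking and punching, and asks whether the PIRA changes its incidence. A child lying still and asleep is the opposite of that picture. Yet a nurse who fills in Figure 3 literally for such a child records a total that meets the ED definition. The wording in D(3) implies that some children are not yet awake when they reach the PACU, so the arrival wording in D(5) makes this reachable.

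Extraction is retrospective. Without a written rule, the person reading the chart has no instruction for separating a 12 that reflects sleep from a 12 that reflects delirium.

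The ED part of Aim 3 is at stake. Counting sleep as ED raises the rate in both arms and pulls the arms together. It could distort the comparison further if the share still asleep differs between arms. The nurse's blinding does not prevent that, because the cause would be the child's state and not the rater's expectation.

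**Working it through.** **1. Reproduce the scale.** Inputs are the item scores in Figure 3 and the summing rule in D(5). Five items with five levels give 5^5 = 3,125 response patterns. Their totals run from 0 to 20, which agrees with Table 1 and D(5).

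**2. Score the quiet, unresponsive child.** With Not at all on every item:

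4 (eye contact) + 4 (purposeful) + 4 (aware) + 0 (restless) + 0 (inconsolable) = 12.

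This meets ≥ 12 and does not meet > 12.

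**3. How narrow is the problem?** There are 5^3 = 125 patterns with both restless and inconsolable at 0. Their highest total is 12, and only the pattern in step 2 reaches it. One step of improvement on any reverse-scored item gives 3+4+4+0+0 = 11, below the threshold. So ≥ 12 admits one quiet pattern, the one a still, sleeping child produces, and > 12 admits none.

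**4. Would > 12 settle it?** Not entirely. An unresponsive child who is restless at the lowest positive level scores 4+4+4+1+0 = 13 and still counts. That child is no longer quiet, but may still not be awake.

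**5. Effect on the comparison.** Let s be the share of an arm scored while asleep, each such child scoring 12, and let p be the true ED rate among the rest. Then

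observed ED = s + (1 − s)p,

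and with equal s in both arms

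observed difference = (1 − s)(p_control − p_PIRA).

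D(4) quotes 30–50% ED in most studies; 40% is taken for control. The 20% for PIRA and all values of s are assumptions.

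- s = 0: 40% vs 20%, difference 20 points.
- s = 10%: 0.10 + 0.90×0.40 = 46%; 0.10 + 0.90×0.20 = 28%; difference 18 points.
- s = 25%: 0.25 + 0.75×0.40 = 55%; 0.25 + 0.75×0.20 = 40%; difference 15 points.
- s = 40%: 0.40 + 0.60×0.40 = 64%; 0.40 + 0.60×0.20 = 52%; difference 12 points.

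**6. Unequal asleep shares (hypothetical).** Take 20% asleep in control and 35% in PIRA.

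- True 40% vs 20%: control 0.20 + 0.80×0.40 = 52%; PIRA 0.35 + 0.65×0.20 = 48%. The difference falls from 20 to 4 points, with its direction kept.
- True 40% vs 30%: control 52%; PIRA 0.35 + 0.65×0.30 = 54.5%. The direction reverses, but only because the assumed true effect is smaller.

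**The case against.** The strongest reply is that nobody scores a sleeping child. D(5) also ties the PAED to emergence, D(3) speaks of awakening, and D(5) says that the assessors are trained for reliability. Read together, these favor scoring at awakening, and then the problem does not arise. This stands to the extent that the documents do not show that sleeping children are in fact scored. A reader might infer that the plan counts sleep as ED as a matter of course. The text supports only that the rule permits it. Training in the scale does not supply an awake condition that is written nowhere, and nothing says which of the timing statements governs.

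A second reply is that only one of the 125 quiet patterns is affected. That is correct, but it is the pattern expected of a still, sleeping child.

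A third is that the fault lies in the cut-off and not the timing. In part it does: moving from the cited > 12 to ≥ 12 is what brings the quiet child in. But step 4 shows that the cut-off alone does not deal with every child who is not awake.

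A reader might also infer that the misclassification would reverse a real benefit. The documents do not support this. It needs unequal asleep shares, which they do not report, together with a smaller true effect; under 40% vs 20% with the same shares, the direction is kept.

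Finally, ED is secondary in a pilot, section H names no test for it, and section I powers the trial on mYPAS. Even with no misclassification, 40% vs 20% at 30 per arm has only about 39% power. Lost power is therefore not the main argument. The point concerns the meaning of the reported rates and of their difference.

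**Conclusion.** The point holds as a defect in the outcome definition. As written, Figure 3 and the ≥ 12 rule class a quiet, unresponsive child as an ED case. The scoring-time statements in D(3) and D(5) do not agree, no awake condition is given, and the accuracy cited in support belongs to a different cut-off. The arithmetic is exact.

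The size of any bias depends on how many children are scored before waking, which the documents do not give. For equal asleep shares above zero and a true ED rate below 100%, ED is inflated in both arms and a true difference keeps only the fraction (1 − s). Over the assumed 10–40%, a 20-point difference becomes 18 to 12 points. If every child is scored awake, there is no bias. The change is worth making because it is cheap. It does not touch the primary outcomes or the mYPAS-based sample size.

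**What to change.** These changes concern the study's outcome definition, extraction and reporting only. PACU care stays as it is.

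1. Reconcile the scoring-time statements in D(3) and D(5), and carry the result into Table 1.
2. Reconcile the ≥ 12 rule in D(5) and Table 1 with the accuracy cited for > 12, and state the reason for the cut-off adopted.
3. Define ED for the study on a score charted once the child is awake, where the chart shows this. Treat a score known to have been taken asleep as not assessable.
4. Report two sensitivity analyses: ED at > 12, which excludes every child with no restlessness or inconsolability; and, where item scores are charted, ED that also requires at least one point from those two items.
5. Report the number not assessable by arm, and keep the analysis of all charted scores alongside.

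The cost is a few sentences in D(3), D(5) and Table 1 and added fields on the extraction form. The real downside is missing data. The protocol does not show that arousal state, item scores or repeat scores are charted, so an awake score may not be identifiable. At the assumed asleep shares of 10–40%, with no later score available, 3 to 12 of 30 children per arm would be lost. If that loss differed by arm, excluding those children would itself introduce selection after randomization, which is why item 5 is needed.

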Using an e-Delphi method to determine important topics to include in such a relational agent, in conjunction with a multidisciplinary team to develop age appropriate dialogue and content, a Pediatric Interactive Relational Agent (PIRA) was created. This PIRA, developed at BCH and programmed with a team at Northeastern University, is the first known relational agent specifically targeting pediatric patients ages 4 through 10 years old and their families, to educate them about anesthesia and the perioperative process prior to their surgical date.

D. Design and Methods

(1) Study Design

This study is a pilot 1:1 randomized trial with one control group and one intervention group. Children age 4 through 10 years and their parents will be randomized to receive the PIRA versus the standard education prior to Otorhinolaryngology (ORL) or Urology surgery. For the purpose of this protocol, “parents” refers to the biological or legally adopted parents or legal guardians. Using surveys, assessments, and data we collect from the medical record and PIRA, we will look at PIRA access and utilization, parental satisfaction and encountered issues with

PIRA, and differences in parental and child preoperative anxiety as well as child emergence agitation between the intervention and control groups.

(2) Patient Selection and Inclusion/Exclusion Criteria

We plan to enroll parents and their children, ages 4 through 10 years old, who are undergoing general anesthesia and elective, outpatient ORL or Urology surgery at BCH Waltham. Children will be American Society of Anesthesiology (ASA) physical status I or II. Parents must be at least 18 years of age or older. Since the study PIRA is currently only available in the English language, both parents and their children must be fluent in English in order to understand and interact with the PIRA.

Parents without reliable internet access to the Google Chrome browser through a tablet or computer, parents of children with diagnosed developmental delays, parents who have children who have had previous surgical history under general anesthesia, and parents of children involved in other anesthesia-related studies at BCH will be excluded for this study. A prior surgery or procedure performed under local anesthesia or without anesthesia (e.g. newborn circumcision, frenulotomy, or newborn Achilles tenotomy), would not exclude the participant. These exclusion criteria will be assessed during the consent phone call.

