A Student's t-test will be used to compare the mean anxiety scores, mYPAS, between the groups. Free text entries from parents will be clarified, consolidated, and summarized by the research team for themes. Quantitative data from the parental preoperative survey will be summarized for mean, median, mode, and standard deviation and presented both numerically and graphically using Microsoft Excel.

I. Statistical Power and Sample Considerations

This pilot protocol is powered to see an effect on pediatric anxiety, as measured by the mYPAS. A sample size of 30 per group will provide 80% power to detect a difference of 6 in mean mYPAS scores between the two groups (assuming a standard deviation for the mYPAS of 8 based on published data in preoperative holding) (Kain et al., 1997), based on Student's t-test and assuming a two-tailed alpha level of 0.05. With a range of 22.5-100, prior studies (Kain et al., 1997) have used a reference score of 37 as consideration for high anxiety cases, with the

prevalence of such high-anxiety cases at 24%. Based on anticipated attrition of 20% due to failure to interact with the PIRA, potential for surgical or anesthesia cancellations before or on the day of surgery, or withdrawal from the study, a total of 76 patients (38 in each group) will be recruited.

J. Study Organization

This study will be directed by [name] and [name], DNP, CRNA with the support of other research team members at Boston Children's Hospital Waltham. The entire research team will be responsible for overseeing patient screening, recruitment and consent. Members of the research team will also be responsible for data collection, data analysis, as well as identifying and reporting adverse events.

Study team members at Northeastern University ([name], BA, PhD Student and [name], BSE, MS, PhD, Associate Dean of Research) were responsible for programming the PIRA and will be monitoring the tool for any technical issues and updating as needed.

Table 1. Outcomes

Outcome	Measurement	Scoring	Timing
Participant Demographics	Age of parent, Gender of parent who completed PIRA, Ethnicity	See Appendix B	Preoperative Waiting, self-reported.
Parental Utilization of PIRA (Primary)	Parental Survey	See Appendix B	Preoperative Waiting, self-reported.

Recommendation to Future Families (Primary)	Parental Survey	See Appendix B Sliding Scale (0 = Definitely NOT Recommended - 10 = Definitely Recommend)	Preoperative Waiting, self-reported.

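### Cheap improvement, not an error: prespecify adjustment of the mYPAS comparison for child age and surgical service, and record both in each arm

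*Combined protocol and SAP*

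**What the plan says.** Section H (Data Analysis Plan) gives one between-group analysis: "A Student's t-test will be used to compare the mean anxiety scores, mYPAS, between the groups". No covariate, regression model or sensitivity analysis is named there or elsewhere.

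Section I bases the sample size on the same test: "A sample size of 30 per group will provide 80% power to detect a difference of 6 in mean mYPAS scores", "assuming a standard deviation for the mYPAS of 8 based on published data in preoperative holding" and "assuming a two-tailed alpha level of 0.05". Section D(4) and Table 1 class child anxiety as secondary.

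Section D(1) describes the design: "This study is a pilot 1:1 randomized trial with one control group and one intervention group". Under D(3), each consenting family is given a one or a two by a random number generator; no stratification or blocking is stated.

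On the population, D(2) says "We plan to enroll parents and their children, ages 4 through 10 years old" and specifies children "undergoing general anesthesia and elective, outpatient ORL or Urology surgery at BCH Waltham". Age and service are therefore settled before allocation for every child. The demographics to be collected (D(4), Table 1, Appendix B) are all the parent's. The one statement that a child's age is entered anywhere, "The child's first name and age will be entered into the PIRA's enrollment page", concerns the PIRA account and so covers the intervention arm only.

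**The concern.** Figure 1 shows that the mYPAS rates behaviour such as play, thumb sucking, babbling and baby talk. It is reasonable to expect such scores to vary with age between 4 and 10. Service is the other eligibility item that divides the sample into distinct groups, although the documents do not say that it predicts anxiety.

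Simple randomisation does not balance either factor by design, and an unadjusted test does not allow for them in the analysis. If they are prognostic, two things are at stake in a comparison of about 60 children: some precision on the one outcome that sets the sample size, and an estimate that carries whatever age or service imbalance happens to arise. Because neither variable is listed for collection in both arms, the team could not readily report whether the arms differed in child age.

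**Working it through.** **Inputs from section I.** Difference 6, SD 8, two-sided alpha 0.05, 30 evaluable per arm, 20% attrition. **Assumed:** R-squared, the share of mYPAS variance explained by age and service together (range 0 to 0.30), and equal arms of 30.

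**1. The plan's own figure.** The standard error of the difference is 8 × √(2/30) = 2.066, so the noncentrality is 6/2.066 = 2.905. With 58 degrees of freedom, noncentral-t power is 81.5%. The smallest n reaching 80% is 29 per arm. For attrition, 30/0.8 = 37.5, rounded up to 38 per arm, or 76 in all. The plan's figures reproduce.

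**2. Adjusted model.** Two covariates leave 56 degrees of freedom. Chance correlation between arm and covariates inflates the variance by an expected factor of 1 + 2/55 = 1.036. The standard error becomes 8 × √(1 − R²) × √1.036 × √(2/30). Counting only the two lost degrees of freedom and omitting this factor would understate the cost.

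| Analysis | SE | Power at difference 6 | 95% CI half-width |
|---|---|---|---|
| t-test | 2.07 | 81.5% | 4.1 |
| Adjusted, R² = 0 | 2.10 | 80.1% | 4.2 |
| Adjusted, R² = 0.05 | 2.05 | 82.0% | 4.1 |
| Adjusted, R² = 0.10 | 2.00 | 84.0% | 4.0 |
| Adjusted, R² = 0.20 | 1.88 | 88.0% | 3.8 |
| Adjusted, R² = 0.30 | 1.76 | 91.8% | 3.5 |

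The half-width is the t quantile (2.002 on 58 df, 2.003 on 56 df) times the SE. Break-even is where (1 − R²) × 1.036 is about 1, that is, R² near 0.035. The worst-case loss is 81.5 − 80.1 = 1.4 points.

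**3. Chance imbalance.** Assume ages uniform over the whole years 4 to 10, which gives an SD of 2. By simulation with 30 per arm, mean ages differ by at least 0.5 year in about 35% of trials and by at least 1 year in about 6%. If one service supplies 50% to 70% of children, its share differs between arms by at least 20 percentage points in about 12% to 15% of trials.

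An imbalance of k SDs in a covariate shifts the unadjusted difference by k × √R² × 8. A 1-year age gap is 0.5 SD: at R² = 0.10 the shift is 0.5 × 0.316 × 8 = 1.3 points, and at 0.20 it is 1.8, against a target difference of 6. A 0.5-year gap at R² = 0.10 shifts it by 0.6.

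**The case against.** The strongest reply is that nothing here is wrong. The planned test matches the power calculation and meets its stated 80%. The trial is a feasibility pilot whose primary outcomes are utilisation and parental impressions. No passage says that age or service predicts the mYPAS, and for service the documents offer no reason at all. If both explain less than about 3.5% of the variance, adjustment gains nothing or loses a little. All of this stands, and it is why the point is an improvement rather than a correction.

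It does not remove the case for adjusting. The loss is capped at about 1.4 points, while the gain is about 2.5 points at an R-squared of 0.10 and 10 at 0.30. Age has support in the wording of the mYPAS items. Covariates also have to be named before the data are seen, since choosing them afterwards invites selection of the favourable model.

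Three stronger readings should be resisted:
- A reader might infer that the unadjusted t-test is biased or the trial underpowered. Over randomisation the test is unbiased and keeps its alpha, and its standard error already reflects chance imbalance.
- A reader might infer that precision is certainly being given away, or that adjusting is free. Both depend on an R-squared that the documents do not give.
- A reader might carry the same model over to the STAI. D(3) lets two parents of one child complete surveys, so a plain linear model could treat correlated responses as independent, and nothing suggests that these covariates predict parental anxiety.

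**Conclusion.** The point holds as an inexpensive improvement to a valid plan. Prespecified adjustment for child age and service improves precision if they are prognostic, and corrects the estimate for the imbalance that actually occurs. At 30 per arm, power moves from 81.5% to between about 80.1% (R-squared 0) and 91.8% (R-squared 0.30). At an R-squared of 0.10 to 0.20, the confidence interval half-width falls from 4.1 to about 4.0 or 3.8 points: useful but modest.

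These figures rest on the plan's difference and SD, equal arms and an assumed R-squared; the imbalance frequencies also rest on assumed age and service distributions. The sample size is not in question. The gap in data collection is the firmer part: child age and service should be recorded in both arms whichever model is used.

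**What to change.** 1. Add child age and service (ORL or Urology) to REDCap at enrolment for every child in both arms.
2. In section H, make the main mYPAS comparison a linear model on arm, child age in years (continuous) and service, reporting the adjusted mean difference with its 95% CI.
3. Keep the Student's t-test as a sensitivity analysis.
4. Leave the recruitment target at 76 and the section I calculation as they stand.
5. Limit the change to the mYPAS.

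The cost is a sentence or two in section H, two fields whose values are already known when eligibility is checked, and at most about 1.4 points of power if the covariates prove useless, which still leaves about the planned 80%. No study procedure changes.
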